5.0 Investigational Plan

5.1 Overall Study Design and Plan: Description

The study is designed to enroll 93 subjects (not including the Japanese sub-study) to meet scientific and regulatory objectives without enrolling an undue number of subjects in alignment with ethical considerations. Therefore, if the target number of subjects has been enrolled, there is a possibility that additional subjects in screening will not be enrolled.

This is a Phase 3, multicenter, randomized, double-blind study designed to evaluate the efficacy and safety of the human anti-TNF monoclonal antibody adalimumab in pediatric subjects with moderate to severe ulcerative colitis (UC).

The present study is to confirm the efficacy and safety of adalimumab in pediatric subjects with ulcerative colitis, in accordance with pediatric legislation in EU and US. The study protocol was reviewed and incorporated comments by the PDCO of the EMA and the FDA.

93 pediatric subjects with moderate-to-severe ulcerative colitis (Mayo Score of 6 to 12 points with endoscopy subscore of 2 to 3, confirmed by central reader) will be enrolled at approximately 50 sites worldwide (Section 5.3.1.1).

There also will be up to approximately 9 Japanese subjects in a Japan sub-study to be enrolled at approximately 10 Japan sites. The Japan sub-study will be conducted utilizing the same design as outlined in the main study with the exceptions that are outlined in a separate Japan specific protocol.

The study will allow enrollment of up to 25% of anti-TNF experienced subjects.

Prior to Amendment 4, subjects who met all of the inclusion criteria and none of the exclusion criteria were enrolled into the study and randomized 3:2 at Baseline to one of two double-blinded adalimumab induction doses (high induction dose or standard induction dose). The randomization was stratified by Baseline disease severity (Mayo Score [≤ 9 , > 9]), prior exposure to infliximab and corticosteroid use at Baseline.

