8.3 Randomization Methods

Prior to Amendment 4, at baseline, subjects were randomized 3:2 to one of the double-blinded adalimumab induction doses (high dose or standard dose). The randomization was to be stratified by baseline disease severity (per Mayo score), prior exposure to anti-TNF, and corticosteroid use at Baseline.

At Week 8, subjects demonstrating a clinical response per Partial Mayo Score (defined as a decrease in PMS ≥ 2 points and $\geq 30\%$ from Baseline) were randomized in a 2:2:1 ratio to one of two adalimumab maintenance treatment groups (standard dose or high dose) or to placebo, respectively. The randomization was stratified according to Week 8 remission status per PMS and induction dose.

After Amendment 4, at Baseline, subjects will receive open-label adalimumab high induction dose.

At Week 8, subjects demonstrating a clinical response per Partial Mayo Score (defined as a decrease in PMS ≥ 2 points and $\geq 30\%$ from Baseline) will be randomized in a 1:1 ratio

to one of two adalimumab maintenance treatment groups (standard dose or high dose). The randomization will be stratified according to Week 8 remission status per PMS.

At or after Week 12, subjects with a disease flare may be re-randomized to receive the blinded-treatments as shown in [Figure 4](#).

The randomization schedule will be prepared by the Statistics Department of AbbVie.

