4.2 Design Diagram

Study M11-290 is a Phase 3, multicenter, randomized, double-blind study designed to evaluate the efficacy and safety of the human anti-TNF monoclonal antibody adalimumab in pediatric subjects with moderate-to-severe ulcerative colitis.

93 pediatric subjects with moderate-to-severe ulcerative colitis (Mayo score of 6 to 12 points with endoscopy subscore of 2 to 3) confirmed by colonoscopy with biopsy or flexible sigmoidoscopy with biopsy were to be enrolled at approximately 50 sites worldwide (Ex-Japan).

[figure not shown]
Prior to Amendment 4, subjects who met all of the inclusion criteria and none of the exclusion criteria were to be enrolled into the study and randomized 3:2 at Baseline to one of two double-blinded adalimumab induction doses (standard induction dose or high induction dose). The randomization was to be stratified by Baseline disease severity (Mayo score $[\le 9, > 9]$), prior exposure to anti-TNF and corticosteroid use at Baseline.

During the randomized double-blind induction period, subjects assigned to high dose (HD) group received adalimumab 2.4 mg/kg (maximum dose of 160 mg) at Baseline and at Week 1. At Week 2, subjects received adalimumab 1.2 mg/kg (maximum dose of 80 mg), followed by a dose of 0.6 mg/kg (maximum dose of 40 mg) at Weeks 4 and 6. Subjects randomized to standard dose (SD) group received adalimumab 2.4 mg/kg (maximum dose of 160 mg) at Baseline and matching placebo at Week 1, adalimumab 1.2 mg/kg (maximum dose of 80 mg) at Week 2, followed by a dose of 0.6 mg/kg (maximum dose of 40 mg) at Weeks 4 and 6.

After Amendment 4, subjects who met all of the inclusion criteria and none of the exclusion criteria were to be enrolled into the study and received open-label (OL) adalimumab high induction dose. During the open-label induction period, subjects received adalimumab 2.4 mg/kg (maximum dose of 160 mg) at Baseline and at Week 1. At Week 2, subjects received adalimumab 1.2 mg/kg (maximum dose of 80 mg), followed by a dose of 0.6 mg/kg (maximum dose of 40 mg) at Week 4 and Week 6.

Ongoing subjects randomized prior to Amendment 4 continued their blinded treatment during the induction period until Week 8.

Prior to Amendment 4, at Week 8, subjects demonstrating a clinical response per Partial Mayo Score (PMS) (defined as a decrease in PMS \geq 2 points and \geq 30% from Baseline)

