4.3 Sample Size

[figure not shown]
The co-primary endpoints will be tested first for the combined high and standard adalimumab dose groups versus external placebo and then individual dose groups versus external placebo separately, controlling the familywise Type I error (multiple significance level) of 5% in a strong sense. For each individual test the nominal power will be calculated.

Assuming a 48% remission rate per PMS at Week 8 for the combined standard and high adalimumab induction dose groups and a remission rate per PMS of 19.83% for external placebo, a total of 77 subjects (presuming HD:SD = 46:31) in ITT-E population (see Section 5.1) provides at least 99% power for a one-sample two-sided Chi-square test using a significance level of 5%.

Assuming a 36% remission rate per Mayo Score at Week 52 for the combined standard and high maintenance dose groups and a remission rate per Mayo Score of 18.37% for external placebo, a total of 57 subjects (presuming HD:SD = 28:29) in the combined adalimumab maintenance dose groups in mITT-E population (see Section 5.1) provide 88% power for a one-sample two-sided Chi-square test using a significance level of 5%.

Assuming that the high adalimumab dose regimen is associated with higher efficacy than the standard adalimumab dose regimen and assuming a 52% remission rate per PMS at Week 8 for the high adalimumab induction dose group and a remission rate per PMS of 19.83% for external placebo, 46 subjects in the high adalimumab induction dose group of ITT-E population provide at least 99% power for a one-sample two-sided Chi-square test using a significance level of 4.95%.

Assuming a 41% remission rate per Mayo Score at Week 52 for the high adalimumab maintenance dose group and a remission rate per Mayo Score of 18.37% for external placebo, a total of 28 subjects in the high adalimumab maintenance dose group of the mITT-E population provide at least 80% power for a one-sample two-sided Chi-square test using a significance level of 4.95%.

Based on the assumption of a 75% response rate at Week 8, 93 subjects were to be included in the study (presuming 12 internal placebo subjects in the maintenance part of the study who were included prior to Amendment 4) to ensure 57 subjects in the combined adalimumab maintenance dose groups.

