For the following subset of endpoints, the double-blind high adalimumab dose will be compared to the standard adalimumab dose on the ITT-E (for Week 8 efficacy endpoints) and mITT-E population (for Week 52 efficacy endpoints) in an exploratory manner at an alpha level 0.05 using a two-sample two-sided chi-square test:

- Proportion of subjects in PMS clinical remission at Week 8;
- Proportion of subjects in Mayo clinical remission at Week 52 in Week 8 responders per PMS;
- Proportion of subjects in Mayo clinical response at Week 52 in Week 8 responders per PMS;
- Proportion of subjects who achieve mucosal healing at Week 52 as measured by Mayo endoscopy subscore (defined as ≤ 1) in Week 8 responders per PMS;
- Proportion of subjects receiving systemic corticosteroids at Baseline who discontinue systemic corticosteroids prior to Week 52* and are in Mayo clinical remission at Week 52 in Week 8 responders per PMS;
- Proportion of subjects in PUCAI remission (defined as < 10) at Week 52 in Week 8 responders per PMS;
- Proportion of subjects in PUCAI response (defined as a decrease in PUCAI
 ≥ 20 points from Baseline) at Week 52 in Week 8 responders per PMS;
- Proportion of subjects receiving systemic corticosteroids at Baseline who discontinue systemic corticosteroids prior to Week 52* and are in PUCAI remission at Week 52 in Week 8 responders per PMS;
- Proportion of subjects in PMS clinical remission at Week 52 in Week 8 responders per PMS;
- Proportion of subjects in PUCAI remission at Week 8;
- Proportion of subjects in PUCAI response at Week 8.

*discontinued systemic corticosteroids prior to Week 52: stop date of corticosteroid must be before the min (nominal day of Week 52 per Visit Window table, visit date at which the endpoint was measured).

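### The exploratory high-versus-standard dose comparisons specify no confidence interval for the dose difference, and at Week 52 the chi-square omits the one factor that stratified maintenance randomization throughout (minor)

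*SAP*

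**What the plan says.** SAP 10.4 lists 11 binary endpoints on which the double-blind high dose is compared with the standard dose "in an exploratory manner at an alpha level 0.05 using a two-sample two-sided chi-square test". Three are Week 8 endpoints on ITT-E. Eight are Week 52 endpoints on mITT-E: six in all Week 8 responders, and two limited to Baseline steroid users ("Proportion of subjects receiving systemic corticosteroids at Baseline who discontinue systemic corticosteroids prior to Week 52", combined with Mayo or PUCAI remission). No effect measure, interval or stratification is named. Protocol 8.1.4.2 lists the same 11 and names no test.

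SAP 10.1 plans 95% CIs for the proportion in each treatment group. SAP 6.0 has a general sentence on intervals for parameters of interest, but it does not name the dose difference.

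Both randomizations were stratified:

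- **Maintenance** (Protocol 8.3). Before Amendment 4: "The randomization was stratified according to Week 8 remission status per PMS and induction dose". After it: "The randomization will be stratified according to Week 8 remission status per PMS". Week 8 remission status is the common factor.
- **Induction** (SAP 4.2). Baseline Mayo score, "prior exposure to anti-TNF and corticosteroid use at Baseline". Protocol 5.1 instead has "prior exposure to infliximab and corticosteroid use at Baseline".

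SAP 10.7 uses these factors only to form subgroups for the co-primary and ranked secondary endpoints.

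**The concern.** Every confirmatory test sets adalimumab against a fixed external placebo rate. The list in SAP 10.4 is the only place where the SAP tests one randomized arm against another for efficacy. Protocol 5.6.4 says the high regimen was chosen so that a higher exposure could be evaluated, so readers will look here for the answer on dose.

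With about 57 to 77 subjects, a non-significant result is likely even if the assumed dose benefit is real. Without an interval for the difference, a reader could take that result to mean the doses are alike. A test that leaves out a prognostic stratification factor also gives up some of what the stratified randomization provided.

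**Working it through.** **1. The plan's own figures.** SAP 4.3 states power only against external placebo. The normal approximation is Φ[(p1 − p0 − z·√(p0(1−p0)/n)) / √(p1(1−p1)/n)].

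| Test | n | p1 v p0 | Alpha | Computed | Stated |
|---|---|---|---|---|---|
| Week 8 combined | 77 | 48% v 19.83% | 5% | 99.96% | at least 99% |
| Week 52 combined | 57 | 36% v 18.37% | 5% | 88.3% | 88% |
| Week 8 high dose | 46 | 52% v 19.83% | 4.95% | 99.7% | at least 99% |
| Week 52 high dose | 28 | 41% v 18.37% | 4.95% | 81.3% | at least 80% |

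All four reproduce. No power or precision is stated for high versus standard.

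**2. Implied dose difference.** SAP 4.3 gives combined and high-dose rates (for Week 52 high dose, "Assuming a 41% remission rate per Mayo Score at Week 52"), from which the standard-dose rate follows:

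- Week 8 PMS remission: (77×48% − 46×52%)/31 = 42.1%, a difference of 9.9 points.
- Week 52 Mayo remission: (57×36% − 28×41%)/29 = 31.2%, a difference of 9.8 points.

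The other nine endpoints have no planning rates.

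**3. Power of the planned chi-square at that difference** (pooled variance under the null):

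- Week 8: Φ[(0.0994 − 1.96×0.1161)/0.1153] = 13.3%.
- Week 52: Φ[(0.0983 − 1.96×0.1272)/0.1266] = 11.7%.

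**4. Interval for high minus standard at the same rates:**

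- Week 8 half-width: 1.96×√(0.52×0.48/46 + 0.42×0.58/31) = 22.6 points. Wald −12.7 to +32.5; Newcombe −12.3 to +30.7.
- Week 52 half-width: 1.96×√(0.41×0.59/28 + 0.31×0.69/29) = 24.8 points. Wald −15.0 to +34.6; Newcombe −14.4 to +32.7.

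**5. Stratifying at Week 52 by Week 8 remission status.** The documents give no rates by stratum, so these are assumptions. The share of remitters among responders is taken as 48%/75% = 64%.

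Size at a nominal 5%, with equal dose effects:

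| Remission, remitters/others | Chi-square | CMH |
|---|---|---|
| 45/20% | 4.6% | about 5% |
| 50/12% | 3.8% | about 5% |

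Both scenarios average to the planning rate: 0.64×45 + 0.36×20 = 36.0%, and 0.64×50 + 0.36×12 = 36.3%. Exact enumeration with 18 of 28 high-dose and 19 of 29 standard-dose subjects in remission at Week 8 agrees closely: 4.7 v 4.9%, and 3.8 v 4.8%.

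Power, high/standard rates in each stratum, with overall rates near 41/31%:

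| Remitters; others | Chi-square | CMH |
|---|---|---|
| no association | 12.7% | 12.4% |
| 50/40%; 25/15.5% | 11.9% | 12.5% |
| 55/42%; 16/12% | 10.9% | 13.2% |
| 57/44%; 12/8% | 10.2% | 13.6% |

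The second row comes from a fixed-size simulation (57 subjects, 200,000 runs). The others come from a simulation of the two-stage randomization (40,000 runs, Monte Carlo error about 0.2 points). Across the set-ups tried, the loss from CMH with no association was 0.3 to 0.9 points. The change is near zero at a gap of about 25 points between strata, and the gain is mostly up to about 3 points at larger gaps. Adding induction dose as a second stratifier moved power by at most 0.3 points, and the smallest of four strata then averaged 6.4 subjects.

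**6. The other five endpoints.**

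- *Week 8.* Three binary factors make eight strata for 77 subjects. Under assumed prevalences (Mayo above 9 in 35%, prior anti-TNF 20%, steroids 50%) the smallest is expected to hold 2.7. Even with small strata collapsed, power for chi-square v stratified was 14.2 v 13.8% (no association), 13.9 v 13.9% (moderate) and 12.4 v 14.0% (strong).
- *Steroid-free.* If half the subjects are on steroids, about 29 remain. Power was 9.0 v 8.2% with no association and 8.2 v 8.8% in the 55/42%; 16/12% case.

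**The case against.** The strongest reply is that nothing here is an error. The comparisons are labelled exploratory and lie outside the alpha-controlled procedure, and the chi-square is valid. Per-arm proportions with CIs are already planned, so anyone can compute the difference, and the SAP 6.0 sentence could be read to allow an interval. The gain from stratifying rests entirely on assumed rates, and power stays at about 10-15% with either test.

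Most of that stands. It limits the point to specifying and consistently reporting an interval, plus one small improvement in method. SAP 6.0 permits an interval for the dose difference without requiring one.

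Three stronger readings are tempting, and the documents do not support them:

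- *The unstratified test inflates the type I error.* It does not. Under stratified randomization its size falls if strata are prognostic. The high:standard ratio in maintenance was 1:1 both before Amendment 4 (2:2:1 with placebo) and after it, so pooling the two periods does not bias the dose comparison.
- *All 11 tests should be stratified.* Step 6 shows little or no gain for five of them, except under strong assumed association at Week 8, and sparse strata.
- *The 41/31% rates describe all the Week 52 endpoints.* SAP 4.3 gives them for Mayo remission only. Response, mucosal healing and PUCAI endpoints may have quite different rates.

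Nor do the documents plan any equivalence claim. The risk is one of misreading.

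**Conclusion.** The point holds as a minor one. SAP 10.4 specifies a p-value and no interval for the only randomized dose contrast. At the implied difference of about 10 points that p-value has about 12-13% power by direct calculation (10-15% across the scenarios), while the interval of about ±23 points (Week 8) or ±25 points (Week 52) shows plainly how little the data can settle. These figures rest on the SAP's planning rates and cover Week 8 PMS remission and Week 52 Mayo remission only.

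Leaving out Week 8 remission status makes the Week 52 test conservative if that factor predicts outcome. This is plausible, but the documents do not quantify it. The effect on power is small in either direction. No confirmatory conclusion is affected.

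**What to change.** In SAP 10.4:

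1. For all 11 endpoints, report the high-minus-standard risk difference with a 95% CI, naming the method: for example Newcombe, or stratified Mantel-Haenszel where strata are used.
2. For the six Week 52 endpoints in all Week 8 responders, use a CMH test and Mantel-Haenszel risk difference stratified by Week 8 PMS remission status. Keep the chi-square as a sensitivity analysis. State that induction dose is left out because it was a stratifier only before Amendment 4 and would make strata sparse.
3. Keep the chi-square for the three Week 8 and two steroid-free endpoints. The anti-TNF versus infliximab wording then does not affect these analyses.

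The cost is some SAP wording and a few table columns, with no new data. If Week 8 remission status turns out not to be prognostic, the loss is under 1 point of power. The SAP addendum of March 2020 describes analysis already performed. If these comparisons have also been run, the differences and intervals can still be added, with the stratified test labelled post hoc.

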10.5 Handling of Multiplicity

The sequentially rejective multiple test procedure for the co-primary and ranked secondary endpoints will ensure that the familywise Type I error (multiple significance level) of 5% is controlled in a strong sense for confirmatory analysis.

10.6 Efficacy Sensitivity Analyses

[figure not shown]
Sensitivity analyses of the co-primary and ranked secondary endpoints based on OC, mNRI, LOCF and MI (see Section 6.0) will be conducted as applicable. Moreover, the PP population will be used for a sensitivity analysis of the co-primary and ranked secondary endpoints based on NRI.

Additional sensitivity analyses may be performed as deemed appropriate.

10.7 Efficacy Subgroup Analysis

The subgroups listed below will be used for analysis of co-primary and ranked secondary endpoints including calculation of 95% CIs.

- Sex (male, female)
- Age ($< 13 \text{ years}, \ge 13 \text{ years}$)
- Ethnicity (white, non-white)
- Geographic region (North America, Western Europe, Eastern Europe)
- Disease severity per Baseline Mayo Score* $(\le 9, \ge 9)$
- Prior exposure to anti-TNF* (yes, no)
- Baseline systemic corticosteroid use* (yes, no)
- Baseline IMM use (yes, no)
- Weight ($< 40 \text{ kg}, \ge 40 \text{ kg}$)
- Pancolitis (yes, no)

- Disease duration (≤ Baseline-median, > Baseline-median)
- Baseline hs-CRP (≤ Baseline-median, > Baseline-median)
- Fecal calprotectin (\leq Baseline-median, \rightarrow Baseline-median)
- Induction treatment group* (I-HD, I-SD, I-HD-OL) [only for Mayo clinical remission at Week 52 in the mITT population]
- Week 8 remission status per PMS* (yes, no) [only for Mayo clinical remission at Week 52 in the mITT population]

*the true information from EDC to be used and a footnote to be added for cases where these values are discrepant to the values from IRT.

For the RR population Mayo clinical response and remission at Week 52 by treatment groups with vs. without re-induction dose after disease flare (as defined in Section 5.1) will also be summarized.

[figure not shown]
